 - The medical students and attendings that are CITI certified and are members of the research team will have access to:
 - o REDCap or Qualtrics or similar database
 - o EPIC chart
 - Paper documentation
 - They will see PHI and will not be blinded
 - The medical students and attendings who are not CITI certified OR are not members of the research team will be have access to:
 - EPIC chart, when appropriate for direct patient care
 - Will document in the paper chart and then will hand over the information to the research team.
 - May request access to the paper documentation
 - Support staff for this research project, including but not limited to the statistician will have access to:
 - o REDCap or Qualtrics or similar database to help compile data
 - 25

6. Describe the plans for destruction/removal of identifiers. (Identifiers should be removed at the earliest opportunity.) (If you requested a partial waiver of HIPAA Authorization for screening purposes in Section 12 by marking Box 1, please mark OTHER and explain that identifiers will be destroyed after data collection.)

☑ End of study
 □ Years after study completion
 □ Other (specify)

Consider the following when answering item 6:

- The consent document must describe if or when and how the data will be de-identified or destroyed, or if identifiers will be maintained.
- Investigator must adhere to sponsor requirements or procedures outlined in the grant, if applicable.
- If the research involves a waiver of authorization, to conform to the HIPAA regulations
 accounting requirements related to a waiver of authorization [Privacy Rule, 45 CFR Part 164];
 please indicate that records (including the documentation of waiver approval) will be
 maintained for a minimum of 6 years following study completion.

SECTION 15: SUBJECT RECRUITMENT

1. How will potential subjects be initially identified for this research study?

⊠PI/collaborators will recruit their own patients (face to face)

Advertisements/media. All material must have IRB approval. See attached

 □ Registry or bank (either pecimens or data) Is it an IRB-approved registry?
 □ No
 □ Yes - If YES, IRBNet #:

Query of records (e.g.: medical, employment, school) (You MUST request a partial waiver of HIPAA Authorization for screening purposes in Section 12, B box 1 by completing C1a and C2.)

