 - The attendings providing care to the newborns all have newborn admitting privileges and would be expected to either provide emergent care immediately themselves or call for assistance.
 - UnityPoint Health Methodist and/or OSF St. Francis Medical Center has onsite 24/7 neonatology specialists as well.
- 3. Is the language explaining provisions for medical care in the consent document? $\hfill\squareNo$

⊠Yes

4. Will there be a data safety monitoring board (DSMB)/ Data Monitoring Committee (DMC) assigned to this study?

27

 \boxtimes No - If **NO**, skip to Question 5.

□ If **YES**, describe the DSMB/DMC structure and meeting plan (for example: how often they will meet) and how the findings will be reported back to the individual investigators and the IRBs.

5. Does the research protocol have a data and safety monitoring plan?

□ Not Applicable. All of the following criteria are met: research is minimal risk, does not involve physical or therapeutic intervention with subjects, subject trauma or distress is not an anticipated risk and the sponsor does not require a monitoring plan.

⊠No - If NO, please describe the methods to be used in this study to monitor the ongoing safety of the subjects (please refer to the paragraph below for information to be provided.)

□Yes - If YES, please describe the data safety monitoring plan in detail here:

Data and safety monitoring plan should contain the following: safety information (including serious adverse events) to be collected, methods for collecting information (e.g., case report forms, at study visits, by telephone calls), frequency of data collection, frequency of cumulative safety data reviews, responsibility for oversight and reporting of safety data, if applicable, statistical tests for analyzing the safety data to determine if harm is occurring when not using DSMB and, if applicable, conditions that trigger an immediate suspension of the Research.

- Built in to our protocol is a way for any practitioner who is involved in the direct patient care of any of our subjects to reach out to the research team to request documentation of the procedures performed. This would reveal if the subject was in the control or treatment arm.
- Any inquiry of this sort will be further investigated by the research team, including but not limited to:
 - o Inquiring about adverse reaction
 - o Determining if the participant was in the control or treatment arm

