 - Further investigation as deemed necessary if the participant was in the treatment arm
- Because there is a paucity of research in this area, all report adverse reactions will be taken seriously and investigated
- Hazard ratios will be assessed

6. Is this a multi-center trial?

□No

⊠Yes

7. Is your site the lead site or serving as the data coordinating center?

□No----NA

□Yes - If **YES**, describe the plan for managing and communicating the following information among the multi-center sites:

- Unanticipated problems involving risks to subjects or others-The PI is available 24/7 for discussion of any unanticipated outcomes. The PI is responsible for communicating all outcomes to the IRB.
- Interim results-Reported yearly as part of scholarly work.
- **Protocol modifications-**The PI sends out updates to the research team when any updates occur to the protocol. This has been clarified through meetings and emails with the research team.
- 8. Will you be applying for a Certificate of Confidentiality? $\boxtimes No$

28

□No - Certificate already in place.

□Yes - If YES, please include this information (as well as any exceptions — for example: mandatory reporting, threats of self-harm) in the consent document. When the IRB approves your research, submit a request for a Certificate of Confidentiality to the appropriate federal agency. After you receive the Certificate of Confidentiality, you must submit an Amendment to the IRB and receive IRB approval. Research subjects may only be enrolled after IRB approval of the Amendment and Certificate of Confidentiality.

9. Does anything you are going to do have any effect on fetal development?
 □Unknown
 ☑ No. This will be performed on newborns.

□Yes

If the answer is YES or UNKNOWN, briefly describe, including a statement in the consent form for a woman of child-bearing potential (if she is presently pregnant or should she become pregnant) describing the risks involved and indicating the safeguards you will employ.

10. To your knowledge, has this protocol been reviewed and subsequently disapproved by any IRB? $\hfill\square$ No

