Randomization: Newborns that are on the lactation rounding list and that meet criteria of our study will be given this brochure and offered admission into the study by the nurse or the lactation specialist caring for the newborn. If the parent is interested in participation in the study, the nurse or lactation specialist will put in a consult for the OMT team and page a member of the research team who will then consent the parent. The newborn will then be single blinded (to lactation) and randomized to either the treatment or control group. No new patients will be enrolled into the study on Fridays as our goal for all the newborns is to have at least *two* treatments before discharge and the OMT research team is only available Monday-Fridays. New enrollment will only occur Monday-Thursdays. Newborns that meet inclusion criteria will then be offered into the research study after obtaining informed consent from the parents. After listing all qualifying newborns alphabetically, newborns will be randomized into treatment/control groups in an alternating fashion.

Protocol for Control Group: Because OMT is a manual therapy, blinding to other participants in the study (lactation team and parents) would be difficult without a sham protocol occurring in the control group. As such, our protocol for the Control Group will be evaluation of cranial strain patterns and cervical motion. These findings will be evaluated, documented, but no corrective treatment will be delivered.

Protocol for Treatment Group: Each newborn in the treatment arm of our research group will receive the same OMT treatment protocol, regardless of somatic dysfunction. The benefits of using a protocol approach are: 1) All OMT providers can be trained and achieve comfort in the treatment options, 2) Eliminates the variable of different treatment options being more/less effective, 3) More accurate information regarding risks/benefits can be communicated to parents, 4) Minimizes inter-researcher outcomes.

The protocol was established by conducting interviews with OMT practitioners both locally and faculty at Osteopathic Medicine faculty at schools in different states. The finalized protocol is as follows:

Protocol:

- 1. Condylar Decompression
- 2. Still Technique to Cervical Region, including the Sternocleidomastoid Muscle
- 3. Balancing of the Hyoid Bone
- 4. Myofascial Release of Thoracic Inlet

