Schedule: The OMT research team will conduct research Monday- Fridays. Newborns meeting criteria will be

34

enrolled on Monday-Thursdays. Treatment or sham treatment for the control group will take place Monday-Friday. The OMT research team will provide treatment and sham treatment to both inpatient and outpatient infants who are enrolled in the study. This will occur in the newborn nursery, patient room, or the lactation office. Residents and attending physicians will provide treatment and sham treatments, all residents will be directly supervised by an attending physician.

Documentation: It is important to blind the lactation team to which newborns receive treatment, as it is lactation who will assign the L.A.T.C.H. scores. In an effort to blind the study, the OMT research team will document in each study participants' chart (regardless of if they are control or treatment group) a Progress Note that read "This newborn is part of the Osteopathic Manipulative Treatment for the Management of Feeding Dysfunction in Breastfed Newborns Research Study. They may be in either the control or treatment group. Their documentation is available immediately by contacting the research team or by looking under Media tab in the next two weeks." This will allow someone to access the information immediately if needed due to any side effects but also allows for blinding of the lactation team.

Scoring and follow up: Infants in both control and treatment groups will have a L.A.T.C.H. assessment at baseline, daily during hospitalization, and at the first two outpatient lactation visits. The L.A.T.C.H. assessment will evaluate Latch, Audible swallow, Type of nipple (mother's nipple), and Hold. While OMT can affect most components of the L.A.T.C.H. assessment, it cannot affect the mother's type of nipple. Therefore, although the L.A.T.C.H. assessment will evaluate the nipple type, this data will not be used in our research. For research purposes the highest L.A.T.C.H. assessment score will be 8 (eight). We will collect baseline, daily assessments, and the two outpatient assessments which will result in 4-5 data points for each infant. These scores will be used to assess the benefit of the addition of OMT to the infants' care plan for feeding dysfunction.

Inclusion Criteria for Subjects.

- Term Infants greater than or equal to 37 weeks gestation
- Level I newborn
- Receiving lactation support
- Identified by lactation as having a newborn component to feeding dysfunction

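### The main safety intake step is a record request that reveals the arm, carries no side-effect condition and does not exclude the lactation staff who score LATCH

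*Protocol*

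**What the plan says.** Section 16, item 5 has the box for no data and safety monitoring plan ticked, so the methods listed beneath it stand in for one. The first is an access right: "Built in to our protocol is a way for any practitioner who is involved in the direct patient care of any of our subjects" to ask for the record of the procedures performed. Its consequence is stated: "This would reveal if the subject was in the control or treatment arm". The follow-up comes next: "Any inquiry of this sort will be further investigated by the research team, including but not limited to" asking whether there was an adverse reaction and establishing the arm.

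Appendix A, under Documentation, sets the blinding aim: "It is important to blind the lactation team to which newborns receive treatment, as it is lactation who will assign the L.A.T.C.H. scores". The same paragraph prescribes a progress note for the chart of every participant in either arm, which tells the reader: "Their documentation is available immediately by contacting the research team". After the text of the note, the protocol explains that access is there in case of side effects, and asserts that the lactation team stays blinded.

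Three other places bear on the point:
- Section 15, items 2 and 3, describe the lactation specialist as one of those looking after the infant.
- The end of item 5 says that reported adverse reactions will all be investigated.
- Section 16, item 7, says: "The PI is available 24/7 for discussion of any unanticipated outcomes".

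**The concern.** LATCH is assigned by an observer, and blinding of the lactation team is the protection that the protocol itself names for it. If a scorer can learn the arm by an ordinary, permitted request, that protection rests on the scorer choosing not to ask.

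The route is open from the first session. It is also most likely to be used for infants whose course prompts a question, so any unmasking need not fall at random. Whether it would differ between arms is unknown, because controls are also handled (evaluation of cranial strain and neck motion).

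The practical weakness is that the safety step and the disclosure of the arm are joined under item 5. That item sets out no intake step that leaves the person raising the question blind.

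**Working it through.** No figure in the protocol bears on this point, so the check is a reading of the passages against each other.

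1. **Who may ask.** Item 5 covers any practitioner in direct care. Section 15 describes lactation specialists as looking after the infant, and Appendix A makes lactation the scorers. On a plain reading the scorers fall within the permission, and no section removes them.

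2. **What the asker learns.** The arm. Item 5 says so itself.

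3. **On what condition.** None is stated. In item 5 the question about an adverse reaction is part of what follows an inquiry, not a test applied before the record is released. Appendix A gives side effects as the purpose of access, but a purpose in the protocol text does not limit release.

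4. **Who is told of the route.** Every reader of the chart, because the note goes into every participant's record. The sentence on side effects lies outside the text of the note, so a chart reader does not see it.

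5. **Against the aim.** The Documentation paragraph says that both goals are met, immediate access and a blinded lactation team. No rule there or elsewhere brings this about for a lactation specialist who asks.

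6. **How many scores are exposed.** Appendix A expects 4 to 5 LATCH scores per infant: baseline, daily in hospital, and two outpatient visits. If baseline precedes the first session (an assumption), a scorer unmasked straight after that session could assign up to 4 − 1 = 3 or 5 − 1 = 4 later scores knowing the arm.

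7. **Size of the bias.** The bias in the mean difference is roughly f × b. Here f is the fraction of infants scored by someone who knows the arm, and b is the shift this causes in the between-arm difference among those infants. The protocol gives neither. Purely as an assumed range, f from 5% to 20% and b from 0.5 to 1.0 LATCH point give 0.05 × 0.5 = 0.025 to 0.20 × 1.0 = 0.20 point. This shows only how the bias would scale. It is not an estimate for this trial.

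**The case against.** The case on the other side is substantial, and much of it stands.

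- **The only route.** A reader might infer that a reaction can be reported only by learning the arm. The text does not support that. Item 5 separately says that reported reactions are investigated, and item 7 gives a principal investigator who can be reached at all times, although in the item on communication among sites. The record request is the main intake step under item 5, not the only contact described.

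- **No safety purpose.** One might also infer that access has no safety rationale. Appendix A states one. What is missing is a condition on release.

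- **Section 14, item 5.** The line "May request access to the paper documentation" can look like a further opening for the scorers. It applies to medical students and attendings who are outside the team or lack the research training. Lactation staff are not in that list, so deleting the line would not protect the score.

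- **Weekend gap.** The statement that "the OMT research team is only available Monday-Fridays" might be read as contradicting the note's promise of immediate access. In Appendix A it explains why there is no Friday enrolment. It concerns sessions and enrolment, and the principal investigator's availability covers contact.

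- **Size as a share of the planned effect.** Dividing an assumed bias by the planning difference of 9.22 − 8.18 = 1.04 mixes scales. Those means come from a cited trial, and 9.22 exceeds the maximum of 8 that this trial uses.

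- **Intent.** The protocol plainly means lactation to be blinded, and prompt access to treatment information is a legitimate safeguard. That is fair, but the intent is not carried into the access rule or into the note that staff read. This last gap is what remains.

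**Conclusion.** The point holds as a conflict between two stated provisions. Section 16, item 5 and the chart note offer a record that discloses the arm, with no side-effect condition and no exclusion of the LATCH scorers. Appendix A requires those scorers to be blinded. The conclusion rests on reading lactation specialists as practitioners in direct care, which Section 15 supports. It does not rest on any passage inviting them to ask, because there is none.

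The size of any bias cannot be computed from the protocol. The sample size of 78 is not affected. The point is worth acting on because the outcome is rated by an observer, the rule works against the blind that the protocol relies on, and the correction is nearly free. The later scan of the paper record into the chart is a separate route to the arm and is not needed for this conclusion.

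**What to change.** Reconcile Section 16, item 5 with the Documentation paragraph of Appendix A:

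1. State that lactation staff who score LATCH may not request, or be given, the procedure record or the arm.
2. State that they and any other practitioner can report a suspected reaction to the research team or the principal investigator without being told the arm.
3. Log each disclosure of the arm: date, recipient and reason.
4. Reword the chart note so that it says access is for side effects and is not for LATCH scorers.

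Access for treating clinicians stays as it is, and Section 14, item 5 needs no change. The cost is a short log and one added sentence in the note.

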 - a. Explain how the use and disclosure of the information presents no more than minimal risk to the privacy of the individual:
 - b. Describe the plan to protect the identifiers from improper use and disclosure (i.e., where will the identifiers will be stored and who will have access):
 - c. Describe the plan to destroy the identifiers at the earliest opportunity consistent with the conduct of the research. If there is a health or research justification for retaining identifiers or if such retention is required by law, please provide this information as well
 - d. Explain why the research could not be practicably conducted without the alteration or waiver:
 - e. Explain why the research could not be conducted without access to and use of the PHI:
 - f. The Privacy Rule requires that when a waiver is granted that only the minimum necessary health information be ACCESSED AND COLLECTED. Therefore, provide justification that the PHI being requested is the minimum necessary information reasonably necessary to accomplish objectives of the proposed research:
- 3. Criteria for Waiver/Alteration of HIPAA Authorization for the MAIN study (complete if B box 2 is marked above)
 - a. Explain how the use and disclosure of the information presents no more than minimal risk to the privacy of the individual: This information will be used by the research team only to 1) identify if the newborn qualifies for admission into the study, 2) identify the correct patient prior to beginning treatment.
 - b. Describe the plan to protect the identifiers from improper use and disclosure (i.e., where will the identifiers will be stored and who will have access): The information will be stored in a password protected document that will be only available to the researchers on the team, all of whom has undergone CITI training. When possible (ie: for the statistician) the information will be deidentified.
 - c. Describe the plan to destroy the identifiers at the earliest opportunity consistent with the conduct of the research. If there is a health or research justification for retaining identifiers or if such retention is required by law, please provide this information as well: All PHI will be held for the duration of the study so that if there are any adverse outcomes we can see if the participant was in the control vs. treatment group. This data will be held as long as deemed necessary by UnityPoint Health and/or OSF St. Francis Medical Center.

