- Data collection will occur through accessing the patients' chart to obtain LATCH scores throughout the study. This will be done through computers and laptops that have been encrypted through UnityPoint Health and/or OSF St. Francis Medical Center- no personal laptops will be used.
- Paper documentation will be held in a LOCKED cabinet in the PI office and will be scanned into the chart after 2 weeks. Once it is scanned into the chart, the paper copy will be destroyed.
- 2. How will data be collected from source documents and incorporated into the research record (paper case report forms, eCRFs, patient diary, eDiary, patient monitoring device, etc.)
 - Data will only be pulled from EPIC and only the patients' LATCH score will be recorded.
- 3. Describe the methods of storage of data (i.e., electronic, hard copy, specimens, artifacts, etc.)
 - A secure database of those enrolled in the study, which arm of the study they are enrolled, and their de-identified number will be stored in REDCap or Qualtrics or similar database
 - Data collection will occur through accessing the patients' chart to obtain LATCH scores throughout the study. This will be done through computers and laptops that have been encrypted through UnityPoint Health and/or OSF St. Francis Medical Center no personal laptops will be used.
 - Paper documentation will be held in a LOCKED cabinet in the PI office and will be scanned into the chart after 2 weeks. Once it is scanned into the chart, the paper copy will be destroyed.
- 4. Describe where each method of data will be stored and how each method will be maintained in a
- secured manner (i.e., encryption, password protection, use of Qualtrics or REDCap, etc.)
 - A secure database of those enrolled in the study, which arm of the study they are enrolled, and their de-identified number will be stored in REDCap or Qualtrics or similar database
 - Paper documentation will be held in a LOCKED cabinet in the PI office and will be scanned into the chart after 2 weeks. Once it is scanned into the chart, the paper copy will be destroyed.
 - REDCap or Qualtrics or similar database will be used for data compilation. Members of the research team will have access
 - Statistician will have access to de-identified data.
- 5. Describe who will have access to each method of data and how each method of data will be transferred to any collaborators.

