OMT is extremely safe and non-invasive. The OMT technique used per the protocol are gentle and indirect. No direct thrusting techniques will be employed. Investigators utilize minimal pressure during these techniques, so that there is no blanching of the investigator's nailbeds. However, as with any medical procedure, OMT carries some risk. Risks associated with the treatments to be used in this study include fatigue, headache, stiffness, tenderness, redness or mild swelling to the area after treatment. If treatment does not work, while patients do not appreciate any benefit they also do not usually show side effects. Patients who respond to treatment often begin feeling better within a day and then noticing improvement of their original symptoms (in this case, improved feeding). Potential benefits of treatment are improved feeding which includes improved latch of the baby, improved swallow, and reduced pain related to feeding for both mom and baby.

Alternative treatments to patients (if applicable).

No alternative treatments to OMT will be offered in addition to the lactation support already provided to breastfeeding infants and mothers who do not need a speech and/or physical therapy consult. Our OMT will augment the current standard for care which includes lactation support. Infants needing a speech and/or physical therapy consult in addition to lactation support will be excluded from the study.

Describe subject compensation, including plans for prorating.

Patients will not be billed for OMT. No monetary patient compensation will be offered

36

Version 3/12/2019 Amended previously on 9/6/2017 for assent of one parent, not two and contact info Created 6/7/2017 Comment [RJ1]: Paper is attached.

Comment [RJ2]: If you think there is a higher attrition rate, the sample size needs to be adjusted.

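### The protocol describes no solicited collection of adverse reactions, so the mild reactions it expects are likely to be under-counted and a low count could not support a safety statement or a usable hazard ratio

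*Protocol*

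**What the plan says.** Section 16 answers No to a DSMB (item 4) and No to a data and safety monitoring plan (item 5). The form then asks how safety will be monitored instead and says what to describe, including "methods for collecting information (e.g., case report forms, at study visits, by telephone calls), frequency of data collection".

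The answer describes one mechanism: "Built in to our protocol is a way for any practitioner who is involved in the direct patient care of any of our subjects" to approach the research team and ask for documentation of the procedures. It continues: "Any inquiry of this sort will be further investigated by the research team". It also states: "Because there is a paucity of research in this area, all report adverse reactions will be taken seriously and investigated". The last line of the answer says that hazard ratios are to be assessed. It names no event, collection method or frequency.

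On data, Section 14, item 2 says: "Data will only be pulled from EPIC and only the patients' LATCH score will be recorded". The list of data sources in Section 13, item 1 leaves interviews and questionnaires unticked. In Appendix A, the scoring and follow-up paragraph schedules LATCH assessments at baseline, daily in hospital and at the first two outpatient lactation visits, and mentions no other item at those contacts.

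On what to expect, the risk paragraph in Appendix A states: "Risks associated with the treatments to be used in this study include fatigue, headache, stiffness, tenderness, redness or mild swelling to the area after treatment". Section 10 gives the same list.

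**The concern.** A system that waits for someone to make contact measures how often people make contact, not how often reactions occur. The listed reactions are the kind such a system tends to miss. They are mild, several are subjective, and a newborn cannot report them. They would often be noticed by a parent, sometimes after the session or after discharge, and they would seldom lead anyone to request a record.

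Two things are at stake. First, a count near zero could be taken as evidence that the treatment is safe when the method was unlikely to detect the reactions in question. Second, the hazard ratio mentioned in Section 16 needs recorded, dated events obtained in the same way in both arms, and the protocol sets up no such collection. A later analysis plan cannot repair this, because reactions that were never recorded cannot be analysed.

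**Working it through.** **Passages side by side**

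| Question | What the protocol gives |
|---|---|
| Which reactions are expected? | Six mild reactions (Section 10; Appendix A, risks) |
| Who asks about them, and when? | Nothing stated; inquiry starts after someone contacts the team (Section 16, item 5) |
| Where are they recorded? | No field stated; only the LATCH score is recorded (Section 14, item 2) |
| What use is planned? | Hazard ratios (Section 16, item 5) |

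The first and last rows require data that the middle two do not provide.

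**Inputs**

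- Group size: Appendix A gives 70 subjects before attrition and 10% attrition. 70 / 0.90 = 77.8, rounded up to 78, or 39 per group. This agrees with the protocol.
- Reaction rates and capture fractions: the documents give none. Every such value below is an assumption. Let c be the share of affected infants whose reaction reaches the research record.

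**What a zero count excludes**

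With no events in n infants, the one-sided 95% upper limit is 1 − 0.05^(1/n).

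- n = 39: 1 − 0.05^(1/39) = 7.4%
- n = 35 (after the planned attrition): 1 − 0.05^(1/35) = 8.2%

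This limits the recorded rate. The limit on the true rate is that figure divided by c. For n = 39:

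- c = 1: 7.4%
- c = 0.5: 7.39% / 0.5 = 14.8%
- c = 0.25: 7.39% / 0.25 = 29.6%

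**Chance of recording nothing among 39 treated infants, assumed true rate 10%**

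The formula is (1 − 0.10 × c)^39.

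- c = 1: 0.90^39 = 1.6%
- c = 0.5: 0.95^39 = 13.5%
- c = 0.25: 0.975^39 = 37.3%

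**What remains for a comparison, assumed true rates 20% (OMT) and 5% (control), 39 per arm**

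| c | Expected recorded events, OMT and control | Total | Power, two-sided Fisher test at 0.05 |
|---|---|---|---|
| 1 | 7.8 and 1.95 | 9.75 | about 40% |
| 0.5 | 3.9 and 0.98 | about 4.9 | about 9% |
| 0.25 | 1.95 and 0.49 | about 2.4 | about 1% |

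For a hazard ratio with equal groups, Schoenfeld's formula gives required events = 4 × (1.96 + 0.8416)² / (ln HR)² for 80% power at two-sided 0.05. With 4 × 7.849 = 31.4:

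- HR 2: 31.4 / 0.480 = 65.3, so 66 events
- HR 3: 31.4 / 1.207 = 26.01, so 27 events
- HR 4: 31.4 / 1.922 = 16.3, so 17 events

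Under these assumed rates, even complete capture falls short of 17. Better collection would therefore make the counts interpretable, but would not make a hazard ratio precise in 78 infants.

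**The case against.** Several stronger readings are tempting, and the documents do not support them.

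- **That a reaction can surface only if a treating practitioner calls.** The promise to investigate reported reactions does not limit who reports. Section 16, item 7 makes the principal investigator reachable at any hour. Attending physicians deliver or directly supervise every session and could see redness or swelling at a repeat session. These routes exist, but all wait for someone to notice and speak up, so they soften the wording and leave the core intact.
- **That nobody asks about reactions at any contact.** This would be inference from silence. The consent pages were removed and may give parents a contact. The submission checklist ticks questionnaires and data extraction sheets that are not shown, and the session documentation described in Section 14 is not reproduced. What can be said is that the text describes no solicited collection and states that only the LATCH score is recorded.
- **That Section 12, item 3c plans a comparison of harm by arm.** It keeps identifiers "so that if there are any adverse outcomes we can see if the participant was in the control vs. treatment group". That is tracing of an individual case. The only text pointing to a comparison is the line on hazard ratios.
- **That the result will be falsely low by a known amount, or that the ratio will be biased.** The capture fractions are assumed. Under-capture that is equal in both arms costs precision but leaves a ratio roughly unbiased.

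It is also fair to say that the trial's objective is feeding outcomes, that the listed reactions are mild, and that serious events in these infants would probably reach clinicians, with neonatology on site. This limits the weight of the point. It does not justify planning a safety statistic on unsolicited reports.

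**Conclusion.** The point holds as an ascertainment weakness in the method the protocol states. No solicited collection of adverse reactions is described, the recorded data are limited to the LATCH score, and hazard ratios are nevertheless planned. Mild reactions are likely to be under-counted, and a low or zero count could support neither a safety statement nor a usable hazard ratio.

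The direction rests on the text and on the nature of the listed reactions. The size does not: the documents give no reaction rate and no capture rate. The widening of the limit after a zero count, from 7.4% to about 15% or 30%, illustrates assumed capture of one half or one quarter and is not an estimate. The feeding comparison itself is unaffected. The change is worth making before or during enrolment, because missed reactions cannot be reliably recovered afterwards.

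**What to change.** Add one short parent question with fixed wording on the listed reactions, identical in both arms, at contacts that already take place. Record yes/no, type and date against the study number, on a form kept apart from the LATCH scorer. Two workable routes are:

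- the research team asks before each later OMT or sham session;
- the parent completes a slip at the outpatient visits, returned to the research team and not to lactation staff.

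The lactation specialist should not ask the question at the LATCH assessment. Answers about tenderness, redness or swelling could reveal the arm to the person who scores the outcome.

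Amend Section 14, item 2 so that this item is part of the recorded data, and list it as a data source in Section 13. Report infants with any reaction by arm as counts and proportions with confidence intervals, in place of reliance on hazard ratios. Keep spontaneous reports as an additional source, shown separately.

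The cost is slightly more data entry and some non-specific reports in both arms. Session staff who ask will know the arm, which is why the wording must be fixed and the LATCH scorer must not see the answers.
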